3. PARTICIPANT SELECTION AND ENROLLMENT PROCEDURES

3.1 Inclusion Criteria

- 3.1.1 Stage IIB-IV mycosis fungoides or Sezary syndrome, who have failed at least 1 standard systemic therapy or are not candidates for standard therapy.
- 3.1.2 Pathology reviewed and the diagnosis confirmed at Stanford University Medical Center.
- 3.1.3 Age > 18 years and ≤ 75 years.
- 3.1.4 Karnofsky Performance Status $\geq 70\%$.
- 3.1.5 Corrected DLCO $\geq 40\%$.
- 3.1.6 Left ventricle ejection fraction (LVEF) $\geq 30\%$.
- 3.1.7 ALT and AST must be ≤ 3 times normal.
- 3.1.8 Total bilirubin ≤ 2 mg/dL unless hemolysis or Gilbert's disease.

If AST and ALT are > 3 to ≤ 5 times ULN, patient may be eligible if:

- 1) Liver biopsy performed within 60 days of HCT excludes active cirrhosis grade greater than 2/4 and bridging fibrosis.
- 2) No clinically evident ascites.
- 3) Patient with Hepatitis B or C are excluded if AST or ALT > 3 x UL.

- 3.1.9 Estimated creatinine clearance \geq 50 ml/min.
- 3.1.10 Have a related or unrelated HLA-identical donor, or one antigen/allele mismatched in HLA-A, B, C or DRB1.
- 3.1.11 Signed Informed Consent.
- 3.1.12 Patients with prior malignancies diagnosed $>$ 5 years ago without evidence of disease are eligible.
- 3.1.13 Patients with a prior malignancy treated $<$ 5 years ago but have a life expectancy of $>$ 5 years for that malignancy are eligible.

3.2 Exclusion Criteria

- 3.2.1 Uncontrolled active infection.
- 3.2.2 Uncontrolled congestive heart failure or angina.
- 3.2.3 Pregnant or nursing patients will be excluded from the study.
- 3.2.4 Those who are HIV-positive will be excluded from the study due to high risk of lethal infection after hematopoietic cell transplantation.

3.3 Donor Inclusion Screening Guideline

- 3.3.1 Age \geq 17.
- 3.3.2 HIV seronegative.
- 3.3.3 No contraindication to the administration of G-CSF.
- 3.3.4 Willing to have a central venous catheter placed for apheresis if peripheral veins are inadequate.

3.4 Donor Exclusion Screening Guideline

- 3.4.1 Serious medical or psychological illness.
- 3.4.2 Pregnant or lactating women are not eligible.
- 3.4.3 Prior malignancies within the last 5 years, except for non-melanoma skin cancers.

3.5 Enrollment

Enrollment occurs when all eligibility criteria are met.

3.6 Informed Consent Process

A conference will be held with the patient and family to discuss this study and alternative treatments available for treatment of the underlying disease. The attending physician will conduct the conference. All potential risks associated with the use of TLI, ATG, immunosuppressive drugs, and allogeneic hematopoietic cell infusions will be discussed as objectively as possible. It will be explained that patients offered this protocol have an underlying malignancy that render them at high risk of relapse or that will result in a significant decrease in life expectancies with conventional treatments. Informed consent from

the patient will be obtained using a form approved by the Administrative Panel on Human Subjects in Medical Research of the Stanford University Medical Center.

3.7 Randomization Procedures

No randomization process will be performed in this study.

4. TREATMENT PLAN

4.1 Investigational Agent or Device Administration

4.1.1 Pre-transplant Evaluation

- a) Prior to initiating therapy, patients will have a complete history and physical examination performed. In addition, a bone marrow specimen and bone marrow aspirate will be obtained for the evaluation.
- b) Patients will have the following laboratory tests performed: CBC with differential, HLA typing, comprehensive metabolic panel, urinalysis, hepatitis panel, HIV antibody, HIV p24 antigen, herpes simplex titer, herpes zoster titer, and CMV titer. Additional evaluation will include a chest radiograph, EKG and pulmonary function testing with spirometry and diffusing capacity. Other testing may be needed and will be determined based on the patients history and physical examination.
- c) HLA typing of the donor will be confirmed at Stanford before beginning treatment.

4.1.2 Allogeneic Transplant: Preparative Regimen

- d) Total Lymphoid Irradiation (TLI) Administration: TLI is administered ten times in 80c- 120c Gy fractions on day -11 through day -7 and day -4 through day -1 according to the above delineated schedule. TLI is administered from a 6 MeV linear accelerator (photon beam). The radiation field (four fields—two anterior and two posterior) will include all major lymphoid organs including the thymus, spleen and lymph nodes. A radiation oncologist will evaluate patients prior to conditioning to determine blocks and radiation ports. TLI will generally be administered between 10 a.m. and 1 p.m. Since TLI can cause nausea, premedication with antiemetic therapy is needed. TLI schedule may be adjusted based on schedule of radiation therapy department.
- e) Anti-thymocyte Globulin (ATG) Administration: ATG will be administered five times intravenously at 1.5 mg/kg/day from day -11 through day -7 for a total dose of 7.5 mg/kg. ATG doses will be based on the adjusted ideal body weight. Premedication for ATG will include benadryl 25-50 mg, Tylenol 650 mg and solumedrol 1.0 mg/kg.
- f) Total skin electron beam therapy (TSEBT) Administration: TSEBT will be given to patients who have extensive skin involvement such as wide spread plaques, tumors, or erythroderma with significant tumor infiltration, as part of cytoreduction prior to transplant. The length of therapy and dose of TSEBT will be determined by the radiation oncologist and individualized based on the patient's presentation and treatment history. In patients receiving TSEBT, TLI will begin during the last two week of TSEBT.
- g) Extracorporeal Photopheresis (ECP) Administration: Extracorporeal photopheresis (ECP) is a leukapheresis-based immunomodulatory therapy that has been approved by the US Food and Drug Administration for the treatment of cutaneous T cell lymphoma (CTCL) since 1988. ECP will be performed using the UVAR XTS Photopheresis System developed by Therakos, Inc (Exton, Pa). Blood (225 mL) will be passed through 3 cycles of leukapheresis, or 125 mL of blood will be passed through 6 cycles, depending on the patient's hematocrit value and body size. At the end of each leukapheresis cycle, the red blood cells and plasma are returned to the patient. The collected WBCs will be mixed with heparin, saline, and 8-methoxypsoralen (8-MOP), which intercalates into the DNA of the lymphocytes upon exposure to UVA light and makes them more susceptible to apoptosis when exposed to UVA radiation. The treated WBC mixture is returned to the patient.

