4.2. General Concomitant Medication and Supportive Care Guidelines.....	17
4.3. Duration of Therapy.....	17
4.4. Duration of Follow Up.....	18
4.5. Criteria for Removal from Study	18
4.6. Alternatives.....	18
4.7. Compensation	18
5. INVESTIGATIONAL AGENT/DEVICE/PROCEDURE INFORMATION	18
5.1. Investigational Agent/Device/Procedure	18
5.2. Availability	19
5.3. Agent Ordering	19
5.4. Agent Accountability	19
6. DOSING DELAYS/DOSE MODIFICATIONS	19
7. ADVERSE EVENTS AND REPORTING PROCEDURES	19
7.1. Potential Adverse Events	19
7.2. Adverse Event Reporting.....	21
8. CORRELATIVE/SPECIAL STUDIES	21
8.1. Laboratory Correlative Studies	21
9. STUDY CALENDAR	22
10. MEASUREMENT OF EFFECT	24
10.1. Anti-tumor Effect.....	24
10.2. Other Response Parameters	24
11. DATA REPORTING/REGULATORY CONSIDERATIONS.....	24
11.1. Monitoring Plan	24
11.2. Stopping Rules	25
11.3. Data Management	25

11.4. Confidentiality	25
12. STATISTICAL CONSIDERATIONS	25
12.1. Endpoints	25
12.2. Analysis Populations.....	26
12.3. Plan of Analysis	26
12.4. Sample Size.....	26
12.5. Interim analyses	27
REFERENCES.....	26

[figure not shown]
APPENDICES

- A. Participant Eligibility Checklist
- B. AE and SAE Reporting Guidelines
- C. Response Criteria in Mycosis Fungoides and Sezary Syndrome

PROTOCOL SYNOPSIS

TITLE	A Phase II Study of Non-myeloablative Allogeneic Transplantation Using Total Lymphoid Irradiation (TLI) and Antithymocyte Globulin (ATG) In Patients with Cutaneous T Cell Lymphoma
STUDY PHASE	II
INDICATION	Advanced Stage Cutaneous T Cell Lymphoma
PRIMARY OBJECTIVES	Clinical Response
SECONDARY OBJECTIVES	Engraftment and GVHD
HYPOTHESES	Graft versus Lymphoma effect provided by Non-myeloablative Allogeneic Transplantation will provide disease control
STUDY DESIGN	Single arm phase II
PRIMARY ENDPOINTS AND SECONDARY ENDPOINTS	Clinical response Incidence of GVHD, EFS, OS
SAMPLE SIZE BY TREATMENT GROUP	40 patients
SUMMARY OF SUBJECT ELIGIBILITY CRITERIA	Advanced stage cutaneous T cell lymphoma patients with HLA-matched related or unrelated donor
INVESTIGATIONAL PRODUCTS DOSAGE AND ADMINISTRATION	Total lymphoid irradiation (TLI) 800 cGy and anti-thymocyte immunoglobulin
CONTROL GROUP	Not applicable
PROCEDURES	Not applicable
STATISTICAL CONSIDERATIONS	Clinical response and incidence of GVHD will be reported as percentage. EFS and OS will be determined using Kaplan-Meier estimation.

SCHEMA

LIST OF ABBREVIATIONS AND DEFINITION OF TERMS

ADL	Activity of daily living
AE	Adverse event
BID	Twice daily

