To apply this novel non-myeloablative regimen of TLI and ATG for allogeneic HSCT, a clinical trial has been conducted in patients with hematological malignancies other than myelodysplasia or myeloproliferative disorders since December 2001. Analysis of the first 37 patients (last patient enrolled in 2004), 19 of whom had NHL, appeared in the New England Journal of Medicine (39). The regimen consisted of 800 cGy in 10 fractions over 11 days with ATG administered at 1.5 mg/kg/d from day -11 to -7. The median age was 56 (28-65) years and 35% had failed prior autologous HSCT. Multi-lineage chimerism was achieved within 56 days and sustained in 31 of 37 patients. Of the 6 who lost their grafts, 4 were in the setting of progressive disease. Minimal neutropenia was observed and more than half of patients did not require hospitalization. Remarkably and in agreement with the preclinical studies, 35 of 37 patients developed no acute GVHD. Among the 18 patients in partial remission at transplant, 10 achieved complete remission, strongly suggestive of retained graft versus tumor effect. Among the 17 patients in complete remission at transplant, 11 continued to be disease-free at 1.5 years. Transplant-related mortality in this study was just 5% at 180 days. To date, 4 deaths due to disease progression and 4 deaths related to the procedure have been recorded. Overall, these results indicate that preparation with TLI/ATG and allogeneic HSCT is well tolerated, associated with prompt multi-lineage engraftment and a markedly low incidence of acute GVHD, with a strong suggestion of retained graft versus tumor effect.

Update on experience in B cell lymphoma patients

Since the initial report, we continue to accumulate the experience using this novel non-myeloablative preparative regimen. To date, we have performed allogeneic HSCT using TLI/ATG preparative regimen in 111 patients. Sixty four of the patients had malignant lymphoma. The majority of the patients (83%) achieved full donor chimerism (> 95% donor cells) and the transplant was well tolerated.

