6. DOSING DELAYS/DOSE MODIFICATIONS

No dose modifications will be made.

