PR	>50% regression in any splenic or liver nodules, or in measurable disease (SPD) in any organs abnormal at baseline. No increase in size of liver or spleen and no new sites of involvement.
SD	Fails to attain the criteria for CR, PR or PD
PD [*]	(1) >50% increase in size (SPD) of any organs involved at baseline or (2) New organ involvement or (3) Loss of response: in those with PR or CR, >50% increase from nadir in the size (SPD) of any previous organ involvement
Relapse	New organ involvement in those with CR

*Use of FDG-PET scan in this instance is compatible with other NHLs but there is a paucity of data in clinical trials of MF/SS to document its utility.

*Whichever criterion occurs first.

Global Response Score

Global Score*	Definition	Skin	Nodes	Blood	Viscera
CR	Complete disappearance of all clinical evidence of disease	CR			All categories have CR/NI
PR	Regression of measurable disease	CR			All categories do not have a CR/NI and no category has a PD
		PR			No category has a PD and if any other category involved at baseline, at least one has a CR or PR
SD	Failure to attain CR, PR or PD representative of all disease	PR			No category has a PD and if any other category involved at baseline, no CR or PR in any
		SD			CR/NI, PR, SD in any category and no category has a PD
PD	Progressive disease				PD in any category
Relapse	Recurrence disease in prior CR				Relapse in any category

NI = non-involved

*It is recommended that not only the proportion of patients who achieve a response or an unfavorable outcome be calculated but a life table account for the length of the interval during which each patient is under observation.

Record of Changes

Date	Protocol Changes	IRB
------	------------------	-----

		Approval Date
March 11, 2009	Original protocol	April 21, 2009
April 29, 2009	Request of the SRC for clarifications in the statistical section	May 19, 2009
June 29, 2009	Changed eligibility criteria related to prior malignancies. Clarified collection goals and processing. Changed CSA taper to begin when chimerism studies obtained. Added timeframes for chimerism evaluations. Added tumor assessments to study calendar. Updated study calendar. Added research sample calendar. Changed fasting before ECP to a low fat diet.	July 14, 2009
March 30, 2010	Decreased TLI from 1200 cGy to 800 cGy. Length of treatment and dose of TSEBT will be determined by the radiation oncologist.	April 20, 2010

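### The synopsis fixes TLI at 800 cGy, but section 4.1.2(d) permits 800 to 1200 cGy; only 80 cGy at every fraction satisfies both

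*Combined protocol and SAP*

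**What the plan says.** The synopsis, under investigational products, gives the dose as one number: "Total lymphoid irradiation (TLI) 800 cGy and anti-thymocyte immunoglobulin".

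Section 4.1.2(d), the instruction that treating staff follow, gives a range per fraction: "TLI is administered ten times in 80c- 120c Gy fractions on day -11 through day -7 and day -4 through day -1". It adds that this is done "according to the above delineated schedule", which is probably a reference to the schema near the front of the protocol. On flexibility, the item says "TLI schedule may be adjusted based on schedule of radiation therapy department". That concerns timing, not dose.

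The table in section 4.3.1 lists the TLI days and shows two fractions on day -1, but gives no dose. Section 6 states "No dose modifications will be made". In the background (section 2.2), the supporting TLI/ATG trial is described this way: "The regimen consisted of 800 cGy in 10 fractions over 11 days".

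**The concern.** The TLI and ATG combination is the experimental conditioning named in the title. In a single-arm study the result describes whatever regimen was delivered, so the protocol needs one statement of the dose.

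As written, a radiation team giving 120 cGy at each fraction would comply with 4.1.2(d) while exceeding the synopsis dose by half. A monitor could not say whether that was adherence or a deviation. The primary analysis set in section 12.2 is everyone who starts conditioning, so the efficacy and safety estimates would pool patients across whatever doses were used.

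The safety case is tied to the lower figure. The 37-patient series in section 2.2 reports 5% transplant-related mortality at 180 days and 35 of 37 patients without acute GVHD, at 800 cGy. Those results do not describe 1200 cGy. In addition, 4.1.2(f) has patients with extensive skin disease start TLI during the final two weeks of total skin electron beam therapy, so for them a second course of radiation overlaps with TLI.

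**Working it through.** **Inputs**

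- Synopsis: total TLI dose 800 cGy.
- Section 4.1.2(d): ten fractions, each 80 to 120 cGy. The unit is oddly spaced in the text; 80 to 120 cGy is the natural reading.
- Section 4.3.1 table: one fraction on each of days -11 to -7, one on each of days -4, -3 and -2, and two on day -1.

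**Step 1: number of fractions.** 5 (days -11 to -7) + 3 (days -4 to -2) + 2 (day -1) = 10 fractions on 9 treatment days. This agrees with the count in 4.1.2(d).

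**Step 2: the synopsis figure.** Total = fractions × dose per fraction. 800 / 10 = 80 cGy per fraction, the bottom of the 4.1.2(d) range and the same as the regimen in section 2.2.

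**Step 3: what 4.1.2(d) permits.** The rows below use the same dose at every fraction.

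| Dose per fraction (cGy) | Total over 10 (cGy) | Excess over 800 cGy |
|---|---|---|
| 80 | 800 | 0 |
| 90 | 900 | 100 (12.5%) |
| 100 | 1000 | 200 (25%) |
| 110 | 1100 | 300 (37.5%) |
| 120 | 1200 | 400 (50%) |

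Because 80 cGy is the minimum, any larger fraction takes the total above 800. The two statements agree only if all ten fractions are 80 cGy. On day -1, with two fractions, the range is 2 × 80 = 160 to 2 × 120 = 240 cGy.

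**Step 4: could a miscount explain the mismatch?** Counting day -1 once gives 9 fractions and a total of 9 × 80 = 720 to 9 × 120 = 1080 cGy. That is still a range, and both the stated count of ten and the double entry on day -1 rule it out.

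**Step 5: is the range a defined option?** Nothing in 4.1.2(d) says so. The radiation oncologist's TLI role there is to set blocks and ports. By contrast, 4.1.2(f) expressly leaves the dose of total skin electron beam therapy to the radiation oncologist's judgement for each patient. The protocol says when a dose is to be individualized, and does not say it for TLI.

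**The case against.** The strongest reply is that the schedule to which 4.1.2(d) defers is missing from the reviewed text. The schema is a figure that did not survive extraction. The February 2017 entry in the Record of Changes mentions a cGy entry with a multiplier of two in the schema, which suggests that it does state fraction doses. Staff may therefore have a clear number in front of them. This stands as a limit on what can be claimed: the documents reviewed do not show that the dose was unclear in practice. It does not remove the conflict. If the schema says 80 cGy, the range in 4.1.2(d) is wrong; if it allows more, the synopsis is wrong.

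Second, the two statements overlap, since 800 cGy lies within the range, and the 50% figure is the extreme case. That is correct. The smallest discrepancy is zero, but it requires the lowest permitted dose every time, and nothing in 4.1.2(d) requires that.

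Third, this can be seen as an editorial slip that touches no statistical quantity. The second half is right: the endpoint, sample size, precision and stopping boundaries are unchanged. The slip would still sit in the operative instruction for a radiation dose, which makes it more than cosmetic.

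Finally, the documents do not show that delivered dose goes unrecorded. No case report form is included, so recording it is a precaution and not the repair of a demonstrated gap.

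**Conclusion.** The concern holds. Two current dose statements conflict by 0 to 400 cGy (0 to 50%), depending on the fraction size used, and no rule chooses within the range. This rests on reading the range in 4.1.2(d) as 80 to 120 cGy and on ten fractions, which two sections confirm. It does not rest on the amendment history.

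That history does offer a likely explanation. The March 2010 entry in the Record of Changes reads "Decreased TLI from 1200 cGy to 800 cGy", and 1200 cGy is exactly 10 × 120, so the upper limit may be left over from the former dose. This is plausible but not established.

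Nothing in the documents shows that any patient was meant to receive, or received, more than 800 cGy. The correction is still necessary, because 4.1.2(d) as written permits a dose that the synopsis excludes and that the supporting 37-patient series did not test.

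**What to change.** Check the schema first. If it gives 80 cGy per fraction, change 4.1.2(d) to ten fractions of 80 cGy, 800 cGy in total, and keep the existing days with two fractions on day -1.

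If larger fractions are intended, amend the synopsis to the range, state in 4.1.2(d) which patients receive them and who decides, and make the schema agree.

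In either case, record the delivered TLI total for each patient so that the report can state the dose actually evaluated.

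The cost is a one-line correction, or a short amendment if the range is meant, plus one recorded data item. No additional patients, procedures or analyses are needed.

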4.1.3 Donor PBPC

- h) Donors will receive G-CSF injections daily from day -5 to day 0. G-CSF will be administered

subcutaneously at a dose of 16 µg/kg/day. Collection of peripheral blood progenitor cells (PBPC's) will be performed by apheresis. Collections generally occur on day -1 and day 0 if needed. CD34⁺ proportion will be evaluated by flow cytometry. Patients will receive all cells collected. The ideal cell doses (based on recipient body weight) for MRD and MUD transplants are > 5x10⁶ CD34⁺ cells/kg. Cells collected on days -1 and 0 will be processed for infusion on day 0. Fresh cells (not frozen) are to be infused whenever possible. Patients will receive premedication approximately 1 hour prior to infusion using current standard of care or as recommended:

- i) Acetaminophen: 650 mg p.o., Diphenhydramine: 50 mg i.v., Hydrocortisone: 100 mg i.v., 1 hour prior to infusion.
- j) For MRD transplants, if the target cell dose is not achieved then a third apheresis procedure may be performed on day +1 and the cells infused on the same day. If after a third apheresis procedure the CD34 dose is <3x10⁶/kg and the total CD3 cell dose does not exceed 5x10⁸/CD3⁺ cells per kg, then a fourth apheresis procedure may be performed on day +2 and the cells infused on the same day. Total CD3⁺ cell dose should not exceed 7x10⁸ CD3⁺ cells/kg. Grafts that contain >7x10⁸ CD3⁺ cells/kg must first be evaluated by the Principal Investigator before infusion. Administration and premedication prior to cell infusion will be identical to those specified for day 0.
- k) Collection of cells for the MUD transplants will be coordinated through the National Marrow Donor Program and subject to the rules of that Program, thus MUD collections will be limited to days -1 and 0 only. If mobilized PBPC is not available through certain NMDP collection centers then bone marrow will be considered.
- l) ABO incompatibility: ABO incompatibility between donor and host will require red cell depletion only if bone marrow is used as the hematopoietic source. Red cell depletion is performed by Hetastarch sedimentation according to standard procedure.
- m) Post-Transplant Growth Factors: Patients should not receive post-transplant growth factors while receiving MMF, particularly during the first month off MMF taper. Growth factors should not be given unless severe neutropenia develops or persists past day 27 post-transplant (ANC < 100/ml for > five days).

4.1.4 Immunosuppression for GVHD prophylaxis

- n) Immunosuppression will include tacrolimus (Prograf) and mycophenolate mofetil (MMF). Tacrolimus will be administered orally at a dose of 0.03 mg/kg/day bid from day -3 through day +56. MMF will begin at 15 mg/kg p.o. bid for MRD and Q 8 hours for MUD from the evening of day 0 to day +27 for MRD or day + 40 with a taper for MUD. Prograf dose adjustments will be made as clinically indicated. Trough levels will be monitored to keep the Tacrolimus level in the range of 8-10 ng/ml. MMF dose adjustments will be made if there is evidence of MMF-related GI toxicity or myelosuppression.
- o) Tacrolimus (Prograf): Tacrolimus is given at 0.03 mg/kg p.o. b.i.d (9 am and 9 pm) from day -3 until after the day +56 chimerism studies have been obtained. Doses should be adjusted to maintain a high therapeutic Tacrolimus level to between 8-10 ng/ml, unless there is renal insufficiency (creatinine >2.0) or hyperbilirubinemia (bilirubin >2.0) in which case the Tacrolimus should be reduced to normalize these parameters. If there is nausea and vomiting at any time during FK506 treatment, Tacrolimus should be administered intravenously by continuous infusion at 3 mg/kg over 20 hours, and adjusted for the Tacrolimus blood level. Tacrolimus will be tapered per standard guideline of Stanford BMT program after the day +56 chimerism studies are obtained. If patient does not tolerate Tacrolimus, tacrolimus may be used and administered per standard guideline of Stanford BMT program.
- p) Mycophenylate mofetil (MMF): Administration of MMF will begin at 15 mg/kg po on day 0, at 5-10 hours after mobilized PBPC infusion is complete. Thereafter, beginning on day +1 MMF is taken at 15 mg/kg po b.i.d. (30 mg/kg/day) if transplantation was using a matched related donor, and 15 mg/kg po Q8 hours if from a matched unrelated donor or a one antigen mismatched donor. Doses will be rounded up to the nearest 250 mg (capsules are 250 mg). MMF will be stopped on day +28 for matched related donors and for one antigen mismatched or unrelated donors beginning day +40. MMF will be tapered by 10% weekly till off, typically by day +96. If there is nausea and vomiting at any time preventing the oral administration of MMF, MMF should be administered intravenously.
- q) Guidelines for MMF dose adjustment: If in the clinical judgment of the investigator, there is documented toxicity related to MMF administration, a dose adjustment will occur. Based on previous solid organ transplantation studies, dose adjustments are likely to occur because of hematopoietic or gastrointestinal adverse effects. Dose adjustments will not be made for hematopoietic toxicities unless severe neutropenia develops or persists until day +21 post-transplantation (ANC <100/ml for >5 days). In the event of gastrointestinal toxicity that requires medical intervention including

medication for control of persistent vomiting or diarrhea that is considered to be due to MMF, a 20% dose reduction or the drug will be given i.v. For severe gastrointestinal toxicity related to MMF (severe refractory diarrhea or overt gastrointestinal bleeding), MMF may be temporarily stopped.

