7. ADVERSE EVENTS AND REPORTING PROCEDURES

7.1 Potential Adverse Events

Tacrolimus

- Human Toxicology: Nephrotoxicity is the most frequent side effect of tacrolimus. Other frequently observed side effects include hypertension, hirsutism, tremors, paresthesias, hepatotoxicity, hypomagnesemia, and hyperkalemia. Transient gastrointestinal symptoms have also occurred, to include anorexia, nausea and ileus. The drug has demonstrated a relative lack of myelotoxicity.
- Pharmaceutical Data Formulation: Tacrolimus is available for oral and intravenous administration. The intravenous solution is available as 1 ml ampules containing 5 mg/ml. Tacrolimus should be administered intravenously over 2-6 hours. Longer infusion times are acceptable and sometimes better tolerated. The contents of the ampules should be diluted 0.9% NaCl injection or 5% dextrose injection
- Supplier: This drug is commercially available.

Mycophenolate Mofetil

- Human Toxicology: The principal side effects include diarrhea, leukopenia, vomiting and infection. The drug is also associated with abdominal pain, nausea, hypertension and anemia.
- Pharmaceutical Data: Mycophenolate Mofetil is available in 250 mg capsules and 500 mg tablets. Mycophenolate Mofetil should be taken on an empty stomach.
- Supplier: Mycophenolate Mofetil is commercially available.

Granulocyte-Colony Stimulating Factor

- Human Toxicology: The primary side effect of G-CSF is bone pain and is more common with higher doses of G-CSF.
- Pharmaceutical Data: G-CSF is available in vials containing 300 μ g or 480 μ g at a concentration of 300 μ g/ml. G-CSF should be refrigerated. G-CSF is given as a daily subcutaneous injection.
- Supplier: G-CSF is commercially available.

Anti-thymocyte Globulin (ATG)

- Thymoglobulin® is a rabbit-thymocyte globulin. It is the purified, sterile, IgG fraction of immune serum of rabbits immunized with human thymus lymphocytes. ATG is a lymphocyte-selective immunosuppressant. It is believed to act by modifying the number and function of lymphocytes.
- Administration: Thymoglobulin® is diluted in 0.9% NaCl. Thymoglobulin® is given intravenously as a 4-

6 hour infusion into a central vein.

- Potential Toxicities: Thymoglobulin® may cause:
Cytopenia of any cell line
Pyrogenic action (ATG causes chills and fever in a high proportion of patients treated)
Fluid retention

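### Section 4.1.4(o) orders intravenous tacrolimus at 3 mg/kg, at least 50 times the oral starting dose in the same item, under the same blood-level target

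*Combined protocol and SAP*

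**What the plan says.** All the dosing text is in Section 4.1.4.

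- **Oral dose.** Item (o): "Tacrolimus is given at 0.03 mg/kg p.o. b.i.d (9 am and 9 pm) from day -3 until after the day +56 chimerism studies". Item (n) attaches both a per-day unit and a twice-daily schedule to the same 0.03 mg/kg. It can be read as 0.03 mg/kg per dose or as 0.03 mg/kg in total per day.
- **Target.** Item (o): "Doses should be adjusted to maintain a high therapeutic Tacrolimus level to between 8-10 ng/ml". Item (n) gives the same range as a trough level. Item (o) also calls for reduction when creatinine or bilirubin exceeds 2.0.
- **Intravenous dose.** The switch applies as follows: "If there is nausea and vomiting at any time during FK506 treatment". The instruction is then "Tacrolimus should be administered intravenously by continuous infusion at 3 mg/kg over 20 hours", "and adjusted for the Tacrolimus blood level". No other intravenous tacrolimus dose, and no separate intravenous target, appears in the document.
- **Intolerance.** Item (o) continues: "If patient does not tolerate Tacrolimus, tacrolimus may be used", following the transplant programme's guideline.

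On toxicity, Section 7.1 states: "Nephrotoxicity is the most frequent side effect of tacrolimus".

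**The concern.** Two routes for the same drug, in the same patient and under the same target, are given amounts that differ by more than an order of magnitude, and the larger one goes directly into the blood. A change of route can justify a lower intravenous dose, because some of an oral dose is not absorbed. It cannot justify a higher one.

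The matter is patient safety rather than inference. Anyone following the text would start a gross overdose of a nephrotoxic drug. The switch is foreseeable: Section 7.1 lists nausea among the effects of tacrolimus and vomiting among the principal effects of MMF. Tacrolimus also starts on day -3, while TLI runs to day -1, and Section 4.1.2 notes that TLI can cause nausea. The document does not say how often the switch is expected.

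**Working it through.** The plan gives no derivation of the intravenous dose and no conversion between routes, so there is no stated calculation to reproduce. The check compares the two stated doses.

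**Inputs**
- Oral dose, item (o): 0.03 mg/kg, twice daily
- Intravenous dose, item (o): 3 mg/kg over 20 hours
- Target, items (n) and (o): 8-10 ng/ml, the only one given

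**Ratio of intravenous to oral starting amount**
- Oral daily amount = 0.03 × 2 = 0.06 mg/kg/day.
- Ratio = 3 / 0.06 = **50**.

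**Other readings of the text**
- Item (n) read as a daily total of 0.03 mg/kg: 3 / 0.03 = **100**.
- Infusion rate carried on for a full day: 3 / 20 = 0.15 mg/kg/h; 0.15 × 24 = 3.6 mg/kg/day; 3.6 / 0.06 = **60**.

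Fifty is the smallest of the three.

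**Can 3 mg/kg be an equivalent dose?** Let F be the fraction of an oral dose that reaches the circulation. With the same clearance by either route, equal exposure requires

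intravenous daily amount = F × oral daily amount, with F ≤ 1.

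From the oral starting dose, the equivalent intravenous amount is therefore at most 0.06 mg/kg/day. The document gives no value for F and none is needed, because the bound holds for every possible value.

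The trough wording in item (n) does not rescue the figure. If the oral trough is 8-10 ng/ml, the average level is at least that high. A steady infusion held at 8-10 ng/ml then needs no more drug than the bound allows.

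Titration does not rescue it either. For 3 mg/kg to match a patient's oral dose, that dose would have to be at least 50 times its starting value, and more than 50 times if F is below 1.

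**Is it an extraction fault?** The entry for November 18, 2014 in the Record of Changes carries the same intravenous figure. The number was not produced by the conversion from PDF. The error lies in the current text of item (o); the log is used only to exclude an artefact.

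**The case against.** **Safeguards exist.** The infusion is to be adjusted to the blood level, and Section 5.4 has central pharmacy keep and monitor the agents. Both may limit harm. Neither changes the written starting dose: adjustment follows once a level is known, item (o) sets no time for the first level on the infusion, and Section 5.4 says nothing about verifying doses.

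**The factor of 50 compares starting doses only.** This stands. A patient who switches later may be taking more or less than 0.06 mg/kg/day. It affects the remedy more than the finding. A fixed ceiling of 0.06 mg/kg/day would be wrong, because it could exceed the current dose of a patient reduced for creatinine or bilirubin. The right limit is the patient's current oral daily dose.

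**The oral daily total is itself unclear.** This also stands. Item (n) can be read as half the amount in item (o). That makes the discrepancy larger and calls for a correction to item (n).

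**Stronger readings a reader might infer**
- *Patients received this dose.* Nothing in the document shows that the infusion was given as written, or that anyone is still being treated.
- *The figure was left over from cyclosporine.* The log records a change from cyclosporine to tacrolimus in items (n) and (o), and the intolerance sentence would fit an incomplete replacement of drug names. This is inference, and the point does not depend on it.
- *The trigger for the switch is also an error.* The MMF rule in item (p) is narrower: "If there is nausea and vomiting at any time preventing the oral administration of MMF, MMF should be administered intravenously". But item (q) also allows intravenous MMF for gastrointestinal toxicity that needs medical intervention, without requiring that oral dosing be impossible. Narrowing the tacrolimus trigger would be a preference.
- *The 20-hour duration conflicts with Section 7.1.* That section gives 2-6 hours but accepts longer infusions, so there is no contradiction.

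**Conclusion.** The intravenous tacrolimus dose in Section 4.1.4(o) is wrong as written and must be fixed. It is at least 50 times the oral starting dose in the same item, and 100 times on the alternative reading of item (n), under a single shared target.

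The conclusion assumes only that the two routes are meant to reach the same 8-10 ng/ml, that clearance does not depend on route, and that no more than all of an oral dose can be absorbed. It needs no outside pharmacokinetic figure. The document does not state the correct intravenous dose, so none is proposed here beyond the upper limit.

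The intolerance sentence, which names tacrolimus as its own substitute, is a lesser slip. It refers to a programme guideline that presumably names the right agent.

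**What to change.** In one amendment to Section 4.1.4:

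1. Item (o): strike 3 mg/kg. Insert a pharmacy-verified intravenous dose that does not exceed the patient's current oral daily dose (0.06 mg/kg/day for a patient still on the starting dose), titrated to 8-10 ng/ml.
2. Item (n): state the oral dose as in item (o), 0.03 mg/kg twice daily.
3. Item (o), intolerance sentence: replace the second mention of tacrolimus with the different agent that the programme intends.

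If any patients are still being treated, send the corrected intravenous dose to the treating team and pharmacy at once, without waiting for the amendment.

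The cost is a wording change to two items and a pharmacy sign-off, with no effect on sample size, endpoints or analyses.
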